## 2. Study Objectives

### 2.1 Study 1

Study 1 will test the central hypothesis that high dose isoflurane anesthesia inducing EEG burst suppression (High ISO/BS+) is a more effective intervention for severe depression when compared to a low dose isoflurane anesthesia that does not induce EEG burst suppression (Low ISO/BS-). The proposed study is a randomized, double-blind trial that will evaluate 30 actively depressed participants with moderate to severe depression. Depression outcomes will be compared between two groups of participants (n=15 per group) who have received 10 treatment applications over a period of three weeks of either High ISO/BS+ or Low ISO/BS-.

Aim 1. To determine whether High ISO/BS+ is more effective than Low ISO/BS- in producing either a treatment response (defined as 50% reduction in depression scores) or full remission of depressive symptoms. We hypothesize that significantly more depressed participants randomized to receive 10 treatments of High ISO/BS+ compared to Low ISO/BS- will show a positive treatment response or full remission by treatment end. Based on the STAR\*D Trial, a responder is a participant showing 50% reduction in depression score and full remission is defined as a score of 0-10 on the HRSD-24 scale and score of 0-5 on the QIDS-SR16.

Aim 2. Preliminary data on neural and immune pathways that are differentially affected by the 2 treatments and associated with antidepressant effects will be explored by comparing changes from pre-treatment to post-treatment in full transcriptome leukocyte gene expression (using the RNA Seq method).

Aim 3. To measure the central neurochemical effects of isoflurane treatment, we will quantify neurotransmitter levels (GABA and glutamate) using magnetic resonance spectroscopy.

### 2.2 Pilot Study 2

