### **4.3 Study Recruitment Procedures**

Potential participants will be recruited to the study through one of three ways: chart review, referral, or direct enrollment.

Recruitment via chart review: Potential participants will first be identified through review of medical records by trained study staff; specifically, examination of the records of patients who have been scheduled for an ECT consultation at the University Neuropsychological Institute (UNI). Participants who may be eligible for screening will be told about the study toward the end of their consultation. Interested patients will be screened and consented either right after the ECT consultation or during a separate appointment.

Recruitment via referral: Physicians from the Department of Psychiatry who have been informed of this study may also refer patients for screening. Patients who are referred will be contacted by study staff to arrange for screening and consent.

Direct enrollment: Psychiatrists listed on the study protocol may identify potential research volunteers during their ECT consultations. These patients will be informed of the research, and if interested, will be screened and consented.

Participants will be informed that there are two study options and that they will be able to decide which one they will participate in. For the isoflurane study, we will explain that some preliminary evidence shows that high dose isoflurane is effective in reducing depression symptoms. However, if the isoflurane study is chosen, there is a 50:50 chance of being in the low dose isoflurane treatment, and the individual will not know what treatment group (high vs low dose) they are in. We do not know whether low dose isoflurane will reduce depression symptoms. For the propofol study, we will explain that this arm of the study is open-label, meaning they will know they are receiving propofol treatment at a dose that produces burst suppression. We will also inform participants that we do not know if propofol treatment will be effective in reducing symptoms of depression.

We hope to enroll at least 1 participant per week and have a maximum capacity of 4 participants per week with a total of 45 participants enrolled in the study (30 in Study 1 and 10 in Study 2).

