## **5.3 Clinical Assessments**

**5.3.1 Primary Response Assessments:** The primary outcome measure is change in depressive symptoms assessed by the Hamilton Rating Scale for Depression (HRSD-24), which is the most widely used method of evaluating the effectiveness of treatments to relieve depression. HRSD-24 will be administered as part of a clinical interview by blinded investigators prior to beginning the treatments, then repeated before treatment #6 and at the end of treatments.

**5.3.2 Secondary Response Assessments to be acquired before each treatment:** Also as standard of care for patients receiving ECT, the participant will fill out the Quick Inventory of Depressive Symptomatology (QIDS-SR) which is a patient self-report measure of depressive symptoms prior to each treatment session. QIDS scores will also be used as a safety measure. If 2 consecutive QIDS scores indicate worsening of depressive symptoms, below pre-treatment values, the study participant will meet with one of the study Psychiatrists to discuss treatment alternatives. The Montreal Cognitive Assessment (MoCA), Generalized Anxiety Disorder scale (GAD-7), and Work and Social Adjustment Scale (WSAS) will be administered prior to beginning the treatments, then repeated before treatment #6, and 48-72 hours post treatment #10.

**5.3.3 Follow-up Assessments to be acquired monthly for up to 6-months post treatment period:** Follow-up assessments will include QIDS-SR, WSAS, and an opened ended question about the participant's experience during the study. Follow-up assessments will be administered over the phone or by email with a link to an electronic survey housed on REDCap (a secure online database). A voicemail may be left (with prior permission) regarding the follow-up assessments.

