### **6.3 Safety and Efficacy Monitoring**

All serious adverse events will be reported within 5 days to the Data and Safety Monitoring Board (DSMB) and IRB by the Principal Investigator or study coordinators. These would include life-threatening cardiac arrhythmias, respiratory arrest, myocardial infarction, stroke, and death. Moderate adverse events including worsening of depressive symptoms will be reported to the DSMB. An interim data analysis will be performed at the midpoint of this pilot investigation, after data is obtained from 5 participants in each of the treatment conditions. The study will be terminated if significantly greater negative outcomes are associated with either isoflurane treatment or propofol treatment.

Prior to each treatment, participants will fill out the QIDS-SR. HRSD-24 will be obtained at baseline, before treatment 6, and after treatment 10. All participants will be assessed before the 6th treatment. If participants in Low ISO/BS- or propofol treatment groups show clinical deterioration (defined by 2 consecutive QIDS scores below baseline OR a decrease in HRSD-24 before the 6th treatment), they will be offered treatment at the 80% burst suppression level (High ISO/BS+) as it has proven effective in reducing depression or ECT as the standard of care treatment. Participants in High ISO/BS+ treatment who show clinical deterioration, as defined above, will be offered ECT. All serious adverse events will be reported within 5 days to the DSMB by the Principal Investigator or study coordinators. The DSMB will also be notified within 10 business days if a study participant is showing signs of clinical deterioration (defined as 2 consecutive QIDS scores below baseline OR HRSD-24 below baseline). Progress reports will be submitted every 6 months. If a participant has a serious reaction to anesthesia, they will be withdrawn from the study.

As exploratory biomarkers, we will evaluate whether quantitative cortical EEG changes early in treatment (obtained from dual lead BIS data in each treatment session) are associated with subsequent remission in depressive symptoms.

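### The deterioration trigger in section 6.3 is reversed, its rescue offer reveals the randomised arm, and either available treatment of acceptors can bias Aim 1

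*Combined protocol and SAP*

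**What the plan says.** - **Trigger.** Section 6.3 defines clinical deterioration twice. For the rescue offer it is "defined by 2 consecutive QIDS scores below baseline OR a decrease in HRSD-24" by the assessment before treatment 6. For notifying the DSMB it is "defined as 2 consecutive QIDS scores below baseline OR HRSD-24 below baseline". Section 5.3.2 begins its own rule with "If 2 consecutive QIDS scores indicate worsening of depressive symptoms", but the clause that follows places worsening below the pre-treatment scores.
- **Offer.** For deteriorating Low ISO/BS- and propofol participants, section 6.3 says "they will be offered treatment at the 80% burst suppression level (High ISO/BS+) as it has proven effective in reducing depression or ECT". For the other randomised arm it says "Participants in High ISO/BS+ treatment who show clinical deterioration, as defined above, will be offered ECT". For the QIDS trigger, section 5.3.2 has a route that does not depend on arm: "the study participant will meet with one of the study Psychiatrists to discuss treatment alternatives".
- **Blinding.** Section 2.1 states "The proposed study is a randomized, double-blind trial that will evaluate 30 actively depressed participants". Section 4.3 has recruits told that "the individual will not know what treatment group (high vs low dose) they are in". Section 5.2 allows access to unblinding information only in a medical emergency and requires any drug disclosure to be recorded. Section 5.3.1 relies on blinded HRSD-24 raters.
- **Analysis.** Section 7.1 compares response and remission at treatment end by treatment group and does not mention rescue. Section 7 excludes anyone with necessary information missing. The withdrawal subsection of section 4.5 stops data collection at withdrawal, except for continuing adverse events. Section 9.1 speaks of alternatives outside the study for participants who worsen.

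**The concern.** Three problems meet in one rule.

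First, it is an operative safety rule in severely depressed patients, and its wording points the wrong way.

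Second, a Study 1 participant who is offered High ISO/BS+ can only have been on Low ISO/BS-. An offer limited to ECT points to High ISO/BS+ for anyone who knows the rule. A participant who hears the offer, declines and stays then gives later QIDS self-reports and HRSD-24 interview answers knowing the arm. A blinded rater does not cure that.

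Third, Aim 1 rests on up to 15 participants per arm, and the plan does not say how someone who accepts rescue is scored. Depending on the reading, people who were doing badly drop out of the denominator, or the effect of the experimental treatment is credited to control.

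**Working it through.** The plan gives no figure on this point to reproduce: the 15 per arm comes without a power calculation or a Low ISO rate. The check is therefore text against text, followed by an illustration.

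**1. Scale direction.** Entry requires HRSD > 18 and QIDS > 10 (section 4.1). Remission is 0-10 on HRSD-24 and 0-5 on QIDS, and response is a 50% reduction (section 2.1). Higher is worse. Taken literally:

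| Course | Section 6.3 as worded | Evident intent |
|---|---|---|
| HRSD-24 lower before treatment 6 | deterioration: rescue offered, DSMB told | improvement: no action |
| Two consecutive QIDS scores lower than baseline | deterioration | improvement |
| Both scores rise throughout | never flagged | deterioration |

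Every HRSD-24 responder at treatment end would also meet the DSMB definition.

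**2. What the offer reveals.**

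| Study 1 arm | Offer in 6.3 | What it reveals |
|---|---|---|
| Low ISO/BS- | High ISO/BS+ or ECT | mention of High ISO/BS+ identifies Low ISO |
| High ISO/BS+ | ECT only | absence of High ISO/BS+ identifies High ISO to anyone who knows the rule |

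The stored code need not be opened for this. Staff titrate to a displayed burst-suppression ratio of 80% or of at most 20% (section 5.1.1), so they already know the arm.

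**3. When it can happen.** QIDS is taken immediately before treatment 1 (section 4.5) and before each later treatment. If the QIDS limb acts on its own, the earliest trigger is the pair of scores before treatments 2 and 3. If the offer belongs only to the assessment before treatment 6, it comes then. Both precede the Aim 1 endpoint.

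**4. What happens to acceptors.** If they leave the study (section 9.1), data collection stops and section 7 excludes them. If High ISO/BS+ is given within the study, section 7.1 scores them at treatment end in the Low ISO group.

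**5. Illustration.** Assumed reference: 11/15 High ISO responders (73%, near the 75% in the earlier open-label study of 8 patients, section 3) and 4/15 Low ISO. Section 4.3 says it is not known whether low dose works, so 4/15 is an assumption, as is every count of leavers and acceptors. With a/n1 High ISO and b/n2 Low ISO responders,

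OR = [a/(n1-a)] / [b/(n2-b)], and SE(log OR) = √[1/a + 1/(n1-a) + 1/b + 1/(n2-b)].

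Reference: OR = (11/4)/(4/11) = 7.56; SE = √(1/11+1/4+1/4+1/11) = 0.826. The comparison is unadjusted.

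| Scenario | High | Low | OR | Wald p | Fisher p |
|---|---|---|---|---|---|
| No acceptors, or two Low ISO acceptors who do not respond and are scored after switching | 11/15 | 4/15 | 7.6 | 0.014 | 0.027 |
| Two Low ISO non-responders excluded | 11/15 | 4/13 | 6.2 | 0.030 | 0.056 |
| One non-responder per arm excluded | 11/14 | 4/14 | 9.2 | 0.012 | 0.021 |
| Three Low ISO and one High ISO non-responder excluded | 11/14 | 4/12 | 7.3 | 0.026 | 0.045 |
| Two switch, one responds | 11/15 | 5/15 | 5.5 | 0.033 | 0.066 |
| Two switch, both respond | 11/15 | 6/15 | 4.1 | 0.072 | 0.139 |

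Excluding l Low ISO and h High ISO non-responders multiplies the OR by [(11-l)/11] × [4/(4-h)]. It falls only if l/11 > h/4. With h = 1 that needs l of at least 3 (3/11 = 0.27 against 1/4 = 0.25).

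**The case against.** **The trigger is a slip that no clinician would follow.** The intent is indeed clear: the term deterioration and the word worsening in section 5.3.2 settle it. A reader might infer that improvers will really be offered rescue, and the documents do not support that. What stands is that a safety rule should not depend on staff correcting it. Section 5.3.2 cannot serve as the correct version, since it too uses below.

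**A rule for acceptors exists.** Section 9.1 suggests that they leave, and exclusion then follows. That is a fair reading, so it would be too strong to say that the plan is silent. But section 9.1 does not settle the High ISO/BS+ offer, and excluding people because they did badly is a poor rule. Complete-case exclusion affects other withdrawals too; this point covers only those created by the offer.

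**Participants may be told about the offer.** The consent pages are not available, so this cannot be checked. Telling them would make the disclosure open, but would not preserve the blind.

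**The numbers are hypothetical.** They are, and p-values near 0.05 differ between Wald and Fisher.

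**A tempting extension** is that the Aim 4 comparison in section 7.3 inherits the same Low ISO rate. It need not: section 7.3 requires a 50% reduction on both HRSD-24 and QIDS, while section 7.1 refers only to depression scores.

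**Conclusion.** The concern holds in three parts. The trigger is reversed in both definitions in section 6.3 and again in section 5.3.2. The Study 1 offer reveals the arm in both directions, against sections 2.1 and 4.3 and the emergency-only unblinding in section 5.2. Acceptors are excluded or scored after switching, and either can bias Aim 1.

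The first two parts follow from the text alone. The size of the third is unknown. With no acceptors, the Aim 1 rates do not change. In the illustration, one or two participants move the odds ratio between 4.1 and 9.2 from a reference of 7.6. A reader might infer that the rule always dilutes the treatment effect. The documents do not support this: High ISO participants can also leave for ECT, and losing one non-responder per arm raises the odds ratio. This is a defect that should be corrected before it is used, not one that invalidates the trial.

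**What to change.** 1. **Trigger.** In both places in section 6.3, change it to two consecutive QIDS scores above baseline or an increase in HRSD-24. In section 5.3.2, replace below by above.
2. **Offer.** In Study 1, use one offer for both arms: the psychiatrist meeting in section 5.3.2, with ECT or other treatment outside the study. Give any High ISO/BS+ only after the end-of-treatment HRSD-24. What is offered remains the sponsor's clinical decision. If it stays arm-specific, have an already unblinded clinician who does no ratings make it, and amend sections 4.3 and 5.2 to allow and record this non-emergency disclosure.
3. **Data.** Obtain the blinded HRSD-24 before the switch where this does not delay rescue, and keep it for those who leave.
4. **Scoring.** In Aim 1, keep acceptors in their randomised arm as non-responders and non-remitters, as a stated exception to the section 7 exclusion. In section 7.3, apply the same rule to both Low ISO and propofol acceptors, using that section's responder definition; applying it to Low ISO alone would tilt the comparison towards propofol.
5. **Sensitivity and reporting.** Vary the acceptors' outcomes, for example by counting 0, 1, 2 and so on per arm as responders. Report offers, acceptances and departures by group.

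The cost is protocol and SAP wording and an occasional earlier interview. There are two real drawbacks. A neutral offer removes one rescue option from Low ISO participants during treatment. Non-responder scoring can favour High ISO if acceptance differs by arm: if one Low ISO acceptor would have responded by staying, 3/15 replaces 4/15 and the odds ratio rises from 7.6 to (11/4)/(3/12) = 11.0. The common offer and the sensitivity analysis limit this.

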### **Subject Withdrawal and Study Completion**

Subject compliance will be monitored throughout the trial by study staff. If any contraindications to the study are identified, participants may be withdrawn by the investigators. Participants can be withdrawn at any point if the investigators feel it is in the participant's best interest or in the interest of study integrity. No information will be collected from withdrawn participants unless it is related to a continuing AE or SAE.

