## **7. Statistical Considerations**

Statistical analyses will employ a statistical mediation model framework. Any participant missing necessary information will be excluded from statistical analysis. Only participants with usable data will be included in the analyses. If the original statistical plan becomes infeasible, the original plan and the modifications made will be reported.

**7.1 Aim 1.** To determine if significantly more depressed participants randomized to receive 10 treatments of High ISO/BS+ will show a positive treatment response (defined as 50% reduction in depression scores) or achieve full remission of symptoms by treatment end compared to those in the Low ISO/BS-group, odds of treatment response and remission will be compared between groups using logistic regression analysis with positive response at treatment end (yes/no) as the dependent variable, and treatment group (High ISO/BS+ vs Low ISO/BS-) as the independent variable. Positive treatment response is defined as 50% reduction in depression scores, and remission will be defined as a score of 0-10 on the HRSD-24 scale.

Covariates will include baseline depression severity and possibly other baseline demographic and clinical measures as needed.

**7.2 Aims 2 and 5.** Using RNA SEQ methods, we will also explore whether participants who respond to treatment show blood-based changes in gene expression of neural and immune pathways previously associated with refractory depression or suicidality by our group or others. A t-test or non-parametric Wilcoxon test will be used, as appropriate. Change from baseline to end of treatment in gene expression levels will be correlated with change from baseline to end of treatment in HRSD-24.

**7.3 Aim 4.** In the open-label trial of propofol, initial evidence of efficacy will be defined by the percent of participants who show at least a 20% reduction in both HRSD and QIDS scores (initial improvement, as employed in the STAR D investigation) and who are propofol/BS+ responders (defined as 50% or more reduction in both HRSD-24 and QIDS scores). Secondary evidence of efficacy will be defined by comparing the percent of participants who are responders to propofol/BS+ vs. to the Low ISO/BS- control condition in the randomized trial.

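### Section 7.3 drops propofol participants who worsen and leave, which inflates the improvement and response percentages, and it does not say how a participant rated after rescue is scored

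*Combined protocol and SAP*

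**What the plan says.** All references are to the combined protocol and SAP.

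- **Rescue (6.3).** For Low ISO/BS- or propofol participants who deteriorate: "they will be offered treatment at the 80% burst suppression level (High ISO/BS+) as it has proven effective in reducing depression or ECT". The trigger is based on consecutive QIDS scores or on the HRSD-24 taken before the sixth treatment. On ratings, the same section says "HRSD-24 will be obtained at baseline, before treatment 6, and after treatment 10", so rescue can start well before the final rating.
- **Withdrawal (Subject Withdrawal and Study Completion).** "No information will be collected from withdrawn participants unless it is related to a continuing AE or SAE". Section 6.3 adds a withdrawal reason not tied to efficacy: "If a participant has a serious reaction to anesthesia, they will be withdrawn from the study".
- **Missing data (opening of 7).** "Any participant missing necessary information will be excluded from statistical analysis", and "Only participants with usable data will be included in the analyses".
- **Aim 4 analysis (7.3).** "initial evidence of efficacy will be defined by the percent of participants who show at least a 20% reduction in both HRSD and QIDS scores", together with the percentage reaching a 50% reduction on both scales. The secondary evidence comes from "comparing the percent of participants who are responders to propofol/BS+ vs. to the Low ISO/BS- control condition in the randomized trial". No denominator is named and rescue is not mentioned.
- **Target (2.2).** The remission goal for the ten-person pilot appears twice: once as at least half, and once, under Aim 4, as a majority. Section 5.1.2 enrols up to 10. Section 7.3 does not analyse remission.

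**The concern.** The people offered rescue are selected for doing badly on propofol. If they leave, the plan removes them from numerator and denominator alike, and the remaining percentage describes only those who did well enough to stay. If they switch to High ISO/BS+ and are still rated, an isoflurane result could enter a percentage meant to describe propofol.

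This bears on the purpose of Study 2. Section 2.2 includes propofol so that a positive Study 1 result is not explained away as an isoflurane dose effect. A propofol rate raised by dropping failures, or by mixing isoflurane back in, is weaker support for that argument. With about ten participants, one or two scoring decisions shift the percentage visibly, so the rule should be settled before results are seen.

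**Working it through.** **The plan's own figure.** Study 2 has no power or sample-size calculation to reproduce. Its only number is the remission target in 2.2: half of 10 is 5.

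**Inputs.** Up to 10 propofol participants (5.1.2). The true response rate and the leaving rate are not in the documents; I assume 40% for the first and show 5%, 10% and 20% for the second. I read deterioration as worsening, although the literal trigger wording in 6.3 refers to scores falling.

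**Step 1: those who leave.** Withdrawal ends outcome collection, so there is no final rating, and section 7 then excludes the participant. Let *p* be the response rate among all treated and *s* the share who leave, all as non-responders. The reported rate is *p*/(1 − *s*):

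| Share leaving | Reported response when the true rate is 40% |
|---|---|
| 0% | 40% |
| 5% | 0.40/0.95 = 42.1% |
| 10% | 0.40/0.90 = 44.4% |
| 20% | 0.40/0.80 = 50.0% |

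In counts, with four responders among ten treated: 4/10 = 40%; one leaver dropped, 4/9 = 44%; two dropped, 4/8 = 50%. The formula applies equally to the 20% improvement percentage.

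**Step 2: those who switch and are still rated.** Suppose two of ten switch and four of the other eight respond. Counting the switchers as failures gives 4/10 = 40%. Taking their final ratings as observed gives anything from 4/10 = 40% (neither responds) to 6/10 = 60% (both respond). Excluding them gives 4/8 = 50%. Section 7.3 does not say which applies.

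**Step 3: the comparison with Low ISO/BS-.** That arm has the same rescue offer, so the bias can go either way. Illustrative counts:

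| Scoring | Propofol | Low ISO/BS- | Difference |
|---|---|---|---|
| Everyone counted, rescue = failure | 4/10 | 3/15 | 20 points |
| Two propofol leavers dropped | 4/8 | 3/15 | 30 points |
| Three Low ISO/BS- leavers dropped as well | 4/8 | 3/12 | 25 points |
| Two propofol leavers dropped; two Low ISO/BS- switchers stay and respond | 4/8 | 5/15 | 17 points |

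**Step 4: the remission target.** I took a true remission rate of 30%, with leavers all non-remitters and dropped (trinomial, n = 10). The chance of reaching at least half is 15% with everyone counted, and 16%, 19% and 29% at 5%, 10% and 20% leaving. If a strict majority is required, the figures are 5%, then 8%, 11% and 18%. So 4/8 meets a target of at least half and fails a target of a majority.

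**The case against.** **The plan already has a rule for leavers.** This is correct: withdrawal and complete-case exclusion together determine what happens to them. The problem there is what the rule does, since it removes people because they did badly. The actual silence concerns participants who take rescue and are still rated.

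**Switchers would not naturally be counted.** Section 7.3 speaks of response to propofol, and Aim 4 of a full propofol course. Someone moved to isoflurane fits neither comfortably, and Risks of Worsening Depression in 9.1 describes options outside the study. A reader might infer that the plan will credit High ISO/BS+ results to propofol. The documents do not support that; they only fail to rule it out. Nor do they say that accepting ECT always means leaving.

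**The documents do not really conflict on the denominator.** A reader might see a contradiction between a sample of ten, a cap of ten and a usable-data rule. These are an objective, an enrolment limit and an analysis rule, and they can coexist. What is missing is the statement in 7.3 of who is counted.

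**The stakes are small.** This stands. The exact 95% interval around 4/10 runs from about 12% to 74%, far wider than a shift of 2 to 10 points. The shift matters because its direction for leavers is predictable and it can be avoided at little cost.

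**Conclusion.** The point holds as a modest one that should be fixed. Following the plan as written drops propofol participants who worsen and leave, and so raises the 7.3 improvement and response percentages: a true 40% response becomes about 42%, 44% or 50% at 5%, 10% or 20% leaving. This rests on leavers being non-responders, on deterioration meaning worsening, and on assumed leaving rates. The switch-and-stay route is possible but not established, and a switcher who does not respond adds nothing to the numerator. The comparison with Low ISO/BS- may be biased in either direction.

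A reader might conclude that exclusion would turn a failed pilot into a successful one, because 4/10 becomes 4/8. The documents do not support that: 2.2 words the target both as at least half and as a majority, 4/8 passes only the first, and 7.3 neither analyses remission nor applies the target. Study 2 is an open-label pilot with no formal test.

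**What to change.** Add to 7.3 only:

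> The denominator is all participants who received the first propofol treatment. A participant who receives a rescue treatment other than the assigned one (High ISO/BS+ or ECT for propofol participants) before the treatment-end assessment, or who has no treatment-end rating, counts as not improved and as a non-responder, and as a non-remitter if remission is reported. Reasons and any post-switch scores are listed separately. In the comparison with Low ISO/BS-, participants in that arm who receive High ISO/BS+ or ECT, or who have no treatment-end rating, are scored by the same rule. For Aim 4 this replaces the section 7 exclusion rule; the complete-case result may be shown as a sensitivity analysis.

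The condition that rescue be other than the assigned treatment is needed so that the rule could never be read as making everyone randomized to High ISO/BS+ a failure. Section 7.1, the randomized analysis, is left unchanged by this point.

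The cost is one paragraph. It needs no extra visits, patients or data after withdrawal. The downsides are that reported percentages may be slightly lower, and that withdrawals unrelated to efficacy, such as a serious anesthesia reaction, count as failures; the listed reasons make these visible. The Low ISO/BS- percentage in 7.3 may also differ from the one behind 7.1, which a footnote can explain.

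### The deterioration trigger in section 6.3 is worded as improvement, and section 7 has no rule for scoring participants who are then rescued or leave

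*Combined protocol and SAP*

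**What the plan says.** **Trigger.** Section 6.3 has deterioration "defined by 2 consecutive QIDS scores below baseline OR a decrease in HRSD-24" before the sixth treatment, and repeats much the same definition for notifying the DSMB. Section 5.3.2 covers the same QIDS event with wording that points both ways: "If 2 consecutive QIDS scores indicate worsening of depressive symptoms, below pre-treatment values".

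**Rescue.** Of Low ISO/BS- and propofol participants who deteriorate, section 6.3 says "they will be offered treatment at the 80% burst suppression level (High ISO/BS+) as it has proven effective in reducing depression or ECT" as standard of care. For the other arm: "Participants in High ISO/BS+ treatment who show clinical deterioration, as defined above, will be offered ECT".

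**Analysis.** Aim 1 (section 7.1) uses "logistic regression analysis with positive response at treatment end (yes/no) as the dependent variable", with treatment group as the independent variable. The general rule in section 7 is: "Any participant missing necessary information will be excluded from statistical analysis". The withdrawal paragraph in section 4 stops data collection after withdrawal, except for continuing adverse events. Section 9.1 (Risks of Worsening Depression) lists ECT among the options after leaving the study.

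**Aim 4.** Section 7.3 counts propofol responders, "defined as 50% or more reduction in both HRSD-24 and QIDS scores", and adds a second comparison, "comparing the percent of participants who are responders to propofol/BS+ vs. to the Low ISO/BS- control condition".

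No section says how a participant who accepts High ISO/BS+ or ECT is scored.

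**The concern.** There are two linked problems.

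First, the trigger points the wrong way. Entry requires HRSD above 18 and QIDS above 10 (section 4.1), and remission is HRSD-24 of 0-10 and QIDS of 0-5 (section 2.1). Lower is better on both scales, so a score that drops from baseline is improvement. Read literally, the rule would offer rescue to people who are getting better.

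Second, even with the trigger corrected, the offered rescue for controls includes the experimental treatment of Aim 1. If a switched control is scored at treatment end, any benefit of High ISO/BS+ is credited to Low ISO/BS-. If people who leave are dropped, likely failures disappear from the denominator, and the arm that loses more of them looks better. The rescue options differ by arm, so the handling can differ by arm too. With 15 per arm, two or three people can change the Aim 1 result, and a scoring rule chosen after seeing the data would carry little weight.

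**Working it through.** **The plan's own figure.** Section 4.5 bases 15 per arm on an earlier study of 8 patients and gives no alpha, power or control rate. There is no power figure to reproduce.

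**Inputs.** From the documents: 15 per arm (section 2.1) and 75% response on High ISO/BS+ (section 3). Assumed: 25% response on Low, two-sided 0.05, three people affected per arm, and the response rate after a switch. The trigger is taken as corrected, and rescued people are assumed not to respond otherwise.

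**Formulas.**
- k Low switched and scored afterwards at response r: Low rate = 0.25 + (k/15) × r.
- k non-responders dropped from an arm with rate p: rate = p × 15/(15 − k), with n = 15 − k.
- Power: the binomial probability of all outcomes with Fisher exact p ≤ 0.05 and High better.

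**True rates 75% v 25% (50 points).**

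| Handling | High | Low | Difference (points) | Fisher power |
|---|---|---|---|---|
| No rescue | 75% of 15 | 25% of 15 | 50 | 68% |
| Three Low switched, scored at 75% | 75% of 15 | 0.25 + 0.2 × 0.75 = 40% of 15 | 35 | 33% |
| Three Low switched, scored at 50% | 75% of 15 | 35% of 15 | 40 | 44% |
| Three Low dropped | 75% of 15 | 3.75/12 = 31.25% | 44 | 53% |
| Three High dropped | 11.25/12 = 93.75% | 25% of 15 | 69 | 98% |
| Three dropped from each arm | 93.75% of 12 | 31.25% of 12 | 63 | 88% |
| Three High dropped, three Low switched at 75% | 93.75% of 12 | 40% of 15 | 54 | 88% |

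Section 7.1 plans logistic regression, which is less conservative than Fisher. An unadjusted likelihood-ratio test gives 81% with no rescue, 49% with three Low switched at 75%, 68% with three Low dropped and 99% with three High dropped. The pattern is the same.

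**No true effect, 50% v 50%: chance of a falsely favourable result (Fisher).**
- No rescue: 0.8%.
- Three High dropped (7.5/12 = 62.5% v 50%): 6.2%.
- Three dropped from each arm (62.5% v 62.5%): 1.0%.
- Three High dropped and three Low switched at 50% (62.5% v 0.50 + 0.2 × 0.50 = 60%): 2.3%.

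**One data set, several answers.** Take 11/15 High and 3/15 Low responders, with four Low non-responders rescued.
- Rescue counted as non-response: 11/15 v 3/15, p = 0.009.
- Scored after rescue, three of the four responding: 11/15 v 6/15, p = 0.14.
- The four excluded: 11/15 v 3/11, p = 0.045.

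**Aim 4.** With an assumed 50% of 10 on propofol, two non-responders switched and scored at 75% give (5 + 1.5)/10 = 65%. Dropping them gives 5/8 = 62.5%.

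**The case against.** **The fate of leavers is inferred.** No sentence says that someone who leaves for ECT is excluded. It follows from reading the withdrawal paragraph, the missing-data rule and section 9.1 together. Section 5.3.1 places the last HRSD-24 at the end of treatments, which could be stretched to cover an early stop. Nor does the plan say that a control given High ISO/BS+ stays in the study. This stands as a limit on the claim, but the uncertainty is itself the gap: the plan does not say which handling applies.

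**The plan leans towards analysis as assigned.** Section 7.1 speaks of participants by what they were randomised to, and section 7 promises to report modifications. Both help. Neither says whether a score taken after a switch counts.

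**The scenarios are severe.** At 75% response only 3.75 of 15 High participants are expected not to respond, so losing three means losing 80% of them. Three of the 11.25 expected Low non-responders is 27%. Dropping a single Low participant leaves power at 68%. This stands, and the figures are illustrations only.

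**Aim 4 is softer.** Its wording does not naturally fit someone moved to isoflurane, and it is an open-label pilot of 10. The rule is still worth stating there.

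**Other scoring is defensible.** Keeping the treatment-end score whatever was received is a legitimate choice. Here, though, it would answer a different question, because the rescue can be the experimental treatment.

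A reader might infer that the plan is biased towards High ISO/BS+. The documents do not support that: dilution and exclusion pull in different directions, and no deterioration or uptake rate is given. A reader might also infer that improving participants will actually be rescued. Section 5.3.2 and section 9.1 show that worsening is meant, so this is a wording error to correct, not evidence of intended practice.

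**Conclusion.** The point holds, and the plan should be changed. The trigger in 6.3 is wrong as written, whatever is decided about scoring. With it corrected, Aim 1 has no rule for participants who accept rescue, and the default readings either credit the experimental treatment to the control arm or remove likely failures.

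Under the stated assumptions, handling alone moves Fisher power from 68% to anywhere between 33% and 98%. In the mixed case that fits the rescue offers most naturally, the apparent difference is 54 points against a true 50, with power at 88%. The false-positive risk is worst (6.2% against 0.8%) only if High alone loses three people; it is 1.0% or 2.3% when both arms are affected. All of this depends on the corrected trigger, an assumed Low response of 25% (50% in both arms for the false-positive figures), assumed numbers rescued, and rescued people not responding otherwise. The documents settle none of these apart from the direction of the trigger.

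**What to change.** 1. In 6.3, define deterioration as two consecutive QIDS scores above baseline, or an increase in HRSD-24 from baseline, in both places where the definition appears. In 5.3.2, replace the reference to values below pre-treatment with wording that plainly means worse.
2. In 7.1, analyse all randomised participants in their assigned arm. Count as a non-responder and non-remitter anyone who accepts High ISO/BS+ or ECT for deterioration, or who is withdrawn for any reason before the treatment-end HRSD-24. This replaces the exclusion rule for Aim 1. Score those who decline rescue and complete as planned.
3. In 7.3, apply the same rule to propofol participants and to the Low ISO/BS- comparator, for both the HRSD-24 and QIDS criteria.
4. As a sensitivity analysis, use the last HRSD-24 or QIDS before the switch. These are already collected before treatment 6 and before each session.

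The cost is a few sentences. The rescue offers stay as they are, no visit or participant is added, and no data are needed after withdrawal.

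The downside is that the endpoint becomes response without rescue or withdrawal, which is slightly conservative for anyone who would have recovered on assigned treatment. If three High participants were rescued, none in Low, and 25% of them would have recovered, High falls to 0.75 − (3/15) × 0.25 = 70% and Fisher power from 68% to 56%. With three rescued in each arm on the same terms (70% v 20%), the difference stays at 50 points and power at 68%.
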